Specific Aim 1: Determine in normal healthy subjects how increased activation of the TC modifies the induction of LTD by 1 Hz and 10 Hz rTMS. Analyses will examine difference scores between sham and active rTMS in the local mean field power (LMFP) of TEPs (Δ LMFP) recorded from TC and DLFC. Parallel groups of healthy subjects (n=5 each) will receive 1 and 10 Hz rTMS. Four contrasts are of interest – (1) sham vs active tDCS for 1 Hz rTMS, (2) sham vs active tDCS for 10 Hz rTMS, (3) 1 Hz vs 10 Hz rTMS for sham tDCS, and (4) 1 Hz vs 10 Hz rTMS for active tDCS. Our working hypothesis is that increased cortical activation will facilitate LTD following rTMS at both frequencies of stimulation, but the effect for 1Hz will be stronger for than for 10 Hz.

Specific Aim 2: Determine in normal healthy subjects how increased activation of the DLFC modifies LTD induced by 1 Hz and 10 Hz rTMS over the TC. New groups of subjects will be recruited. The design, analyses, and predictions are the same as for Aim 1. The difference is that circuits in the DLFC, a functionally connected network, are being preconditioned rather than TC. We predict that rTMS delivered to the TC will induce LTD in the DLFC after it has been preconditioned with tDCS.

Exploratory Aim. We will develop and test a behavioral model of sound perception in healthy participants who have normal hearing by placing them in a sound attenuated environment and measuring ratings of sounds played above threshold. We will examine how tDCS/rTMS modify these perceptions.

Specific Aim 3: Determine in patient with tinnitus how increased activation of the DLFC modifies LTD and tinnitus perception induced by 1 Hz rTMS over the TC. We will recruit ten subjects from a previous study of rTMS for tinnitus (109033) who agreed to be contacted for future research projects. We will examine change from baseline in TEPs (Δ LMFP) recorded from TC and DLFC and on ratings of tinnitus awareness, annoyance and loudness following three days of treatment (tDCS preconditioning of the DLFC followed by 1 Hz rTMS of the TC). Analyses will examine change from baseline for TEPs and tinnitus ratings. Change scores for tinnitus ratings will be compared to those for sham and active rTMS treatments from a previous study (109033).

Aims 1 & 2 Design: A randomized, blinded, sham controlled, mixed effects model with assignment to two treatment arms (1 or 10 Hz rTMS) and three experimental

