Study Title: Regulating homeostatic plasticity and the physiological response to rTMS
PI: [name]
Institution: University of Arkansas for Medical Sciences
Support: Department of Neurobiology and Dev. Scs.

conditions within each arm (Table 1). Subjects will be sequentially assigned to one of two parallel groups (1 Hz or 10 Hz rTMS).

Study endpoints: The primary outcome measure is the local mean field potential calculated for electrodes over the temporal and dorsolateral frontal cortex that are measured at baseline and after sham and active treatment conditions. An exploratory outcome measure is ratings of auditory stimuli detected by participants before and after each of the three experimental conditions.

Statistical Plan or Data Analysis: Aims 1 & 2 examine the effect of treatment dose on one primary outcome measure – a difference score between sham and active rTMS in the LMFP of TEPs (Δ LMFP) recorded from TC and DLFC. The analysis plan is the same for both aims. Hierarchical Linear Models (HLMs) will be used due to the nested structure of the design. HLMs will fit the complex covariance structure of the dosing schedule – sham and active tDCS nested within rTMS treatment frequency (1 Hz and 10 Hz).

Trial design, endpoints and analysis for Aim 3. The design is an open label, feasibility study – a pre-post examination of change in the LMFP of TEPs (Δ LMFP) recorded from TC and DLFC and in the ratings of tinnitus awareness, loudness and annoyance after four days of treatment. Aim 3 is conceptually similar to Aims 1 and 2 in using tDCS preconditioning of rTMS and in using EEG to evaluate change; however, treatment length and the timing and methods of assessing tinnitus were adopted from a previous study so that the data would be comparable.

What are the test articles TMS and tDCS?

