tDCS will be delivered using a Soterix constant current stimulator and Soterix 1 cm diameter Ag/AgCl electrodes powered by two, 9 volt Alkaline batteries. Its current range is 0-2.0mA (in 0.5mA increments). In tDCS, a weak DC electrical current is passed across electrodes located on the scalp to modulate the resting membrane potentials of underlying neurons. The ability of tDCS to control MEP amplitudes in motor cortex is well established.⁸ tDCS delivered at 1 mA and no longer than 20 minutes duration elicits an excitatory effect on underlying tissue beneath the anode electrode (where current is delivered) and an inhibitory effect beneath the cathode electrode (where current is received).⁹⁻¹¹ Multiple studies have used 1 mA tDCS to precondition motor cortex prior to rTMS.^{2;3;12;13} Our approach is different in that 2 mA current will be passed between electrodes for 20 minutes to increase cortical excitability *between* electrodes. At 2 mA and no longer than 20 minutes duration, there is a net increase in excitability under *both* stimulating electrodes.^{14;15} This approach is useful for avoiding the inhibitory effects located beneath the cathode. We adopted this approach to increase cortical excitability homogeneously between electrodes where rTMS will be applied. In this way, we aim to use tDCS to increase the modification threshold of targeted circuits prior to rTMS delivery.

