Our expert consultant, [name], has used MRI-derived finite element models (Soterix HD-Explore software) to map the electrical fields produced by 2 mA tDCS for various electrode locations (Figure 4).¹⁶⁻¹⁸ He determined that by placing the cathode electrode over anterior temporal cortex and the anode over the occipito-parietal junction, the mean field intensity at the site of rTMS delivery in TC can be raised to 0.3 V/m (tDCS often peaks at a field intensity of between 0.3 and 0.5 V/m).¹⁵ By placing electrodes at the F3 and F4 EEG locations in the standard 10/20 system, the mean field intensity over DLFC can be raised to between 0.3 and 0.4 V/m. Importantly, there was minimal overlap between models. So, preconditioning of the TC should not increase activation of the DLFC and vice versa. [name] is currently using 2 mA tDCS for 20 minutes to produce a homogeneous impact on cortical excitability in a large, multisite, phase III clinical trial (The NIA funded ACT study; [name], PI). So, our results will have direct relevance to the largest clinical trial of tDCS ever conducted. Our proposal will take the additional step of pairing tDCS preconditioning with rTMS.

[figure not shown]

Figure 4. Models of electrical current flow through TC and DLFC during 2mA tDCS for 20 minutes. Figure A shows targeted circuit locations in TC and DLFC. Figure B shows relative field intensity in TC with anode located posteriorly and the cathode anteriorly. A white circle denotes approximate C5 electrode location. Figure C shows field intensity changes over DLFC, anode on left and cathode right.

Study Title: Regulating homeostatic plasticity and the physiological response to rTMS
PI: [name]
Institution: University of Arkansas for Medical Sciences
Support: Department of Neurobiology and Dev. Scs.

Differences between tDCS and TMS include presumed mechanisms of action, with TMS acting as neuro-stimulator and tDCS as neuro-modulator. This is an important distinction. Whereas TMS stimulates cortical neurons causing them to fire; tDCS only makes it more or less likely that cortical neurons will respond to further stimulation.

What is the assessment tool TMS/EEG?

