Individual responses to rTMS, both in normal subjects²⁶ and patient populations,²⁷ are variable, which is hard to interpret, in part, because homeostatic plasticity is rarely measured or controlled in rTMS studies.²⁷ Homeostatic plasticity refers to the initial activation state of a synapse, neuron, or population of neurons. rTMS is used specifically to change the initial activation state of neuronal populations – to increase or decrease cortical excitability. In general, high frequency rTMS (>3Hz) is expected to increase cortical excitability by inducing LTP, whereas low frequency rTMS (1 Hz or less) is expected to decrease cortical excitability by inducing LTD. In practice, however,^{3;28} homeostatic plasticity actually determines whether or not rTMS, at any frequency, will induce LTD or LTP. The rationale is based on the Bienenstock-Cooper-Munro (BCM)²⁹ rule of synaptic modification, which holds that a prolonged reduction in post synaptic activity lowers the modification threshold and favors the induction of LTP;

Study Title: Regulating homeostatic plasticity and the physiological response to rTMS
PI: [name]
Institution: University of Arkansas for Medical Sciences
Support: Department of Neurobiology and Dev. Scs.

whereas a prolonged increase in postsynaptic activity raises the threshold and favors induction of LTD. Therefore, either 1 or 10 Hz rTMS can have an excitatory or inhibitory effect depending on the previous activity history of the tissue and where the modification threshold is set at the time of rTMS delivery. These observations are the basis for our central hypothesis that raising the modification threshold, with 2 mA tDCS preconditioning, prior to rTMS delivery, at either 1 or 10 Hz, will facilitate the induction of LTD. The interaction between homeostatic plasticity and rTMS frequency can cause deviations from the usually assumed frequency dependent effects of rTMS (i.e., high frequency rTMS increases and low frequency rTMS decreases cortical excitability). These deviations have undoubtedly produced variability in individual responses to rTMS because the baseline level of cortical excitability is unknown. It is critical, therefore, to develop a method for measuring homeostatic plasticity, which we propose to do using TEPs, and for stabilizing neural activity prior to rTMS delivery, which we propose to do with tDCS preconditioning.

What are the safety concerns associated with using tDCS and TMS in human subjects?

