Several studies have been conducted that combine tDCS and rTMS delivery in the manner we propose for this protocol. No adverse events were reported in these studies. Further the studies confirmed that tDCS is capable of reliably establishing either a low or high modification threshold prior to rTMS.^{2,3,12,36} All of these studies were consistently able to modulate homeostatic plasticity/modification thresholds using tDCS and all studies were consistent in showing that, in line with the BCM rule, homeostatic plasticity determines whether or not rTMS induces cortical inhibition (LTD) or excitation (LTP).

What is unique about our proposal?

Study Title: Regulating homeostatic plasticity and the physiological response to rTMS
PI: [name]
Institution: University of Arkansas for Medical Sciences
Support: Department of Neurobiology and Dev. Scs.

Similar to the above mentioned studies our study uses tDCS to control modification thresholds of targeted brain regions prior rTMS delivery. It differs from these studies, however, in the way tDCS is applied (integrated in an EEG cap for Aims 1 & 2), how cortical excitability is being measured (TMS/EEG rather than MEP recordings), and where preconditioning is targeted (over temporal cortex and dorsolateral frontal cortex rather than over motor cortex). For Aim 3, whereas our previous studies have applied rTMS over the TC for the treatment of tinnitus; this study will add tDCS preconditioning of the DLFC and use a three-day treatment regimen of rTMS. Increasing the modification threshold of circuits in DLFC with tDCS is a means of controlling homeostatic plasticity in a way that promotes LTD induction upon further stimulation. Should stimulation of TC induce LTD in the DLFC, the predicted interaction of these circuits is confirmed. Finally, TMS evoked potentials (TEPs) will be used to physiologically confirm the effects of our interventions by measuring electrical activity directly from the cortex.

Measuring auditory perception before and after the experimental conditions is also a unique feature of this protocol. After 5 minutes in a silent environment, tinnitus-like-perception occurs in the majority of healthy subjects with normal hearing (between 65-94%). In this study, we want to explore whether neuromodulation can alter sound perception in normal healthy subjects. We also want to examine, in patients with tinnitus, how TEPs change in response to treatment as well as tinnitus perception.

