Data collection will be accomplished via case report forms and electronic recording via the devices used in this study. The Principal Investigator will carefully monitor study procedures to protect the safety of research subjects, the quality of the data and the integrity of the study. Participant's data will be de-identified using codes, personal identifiers will be kept separate from study data, and data will be locked in file cabinets or drawers in the TMS laboratory and in the PI's office, if hardcopy, or on a password-protected UAMS server, both located behind locked doors in a restricted access area of the UAMS campus. Only authorized individuals will have access to the code and information that identifies the subjects in this study. Following informed consent to participate, patient's hospital and outpatient records may be reviewed to identify appropriate candidates for the study. Any data obtained as part of the patient's clinical care may be reviewed to determine whether the subject meets inclusion and does not meet exclusion criteria.

Data Analysis

Analyses and Power calculations.

Aims 1 & 2 examine the effect of treatment dose on one primary outcome measure – a difference score between sham and active rTMS in the LMFP of TEPs (Δ LMFP) recorded from TC and DLFC. The analysis plan is the same for both aims. Hierarchical Linear Models (HLMs) will be used due to the nested structure of the design. HLMs will fit the complex covariance structure of the dosing schedule – sham and active tDCS nested within rTMS treatment frequency (1 Hz and 10 Hz). Four primary responses will be estimated, namely Δ LMFP for the sham vs active tDCS and the 1 Hz vs 10 Hz rTMS conditions. From these four responses, four contrasts of interest will be estimated: (1) sham vs active tDCS for 1 Hz rTMS, (2) sham vs active tDCS for 10 Hz rTMS, (3) 1 Hz vs 10 Hz rTMS for sham tDCS, and (4) 1 Hz vs 10 Hz rTMS for active tDCS. An additional 6 contrasts will be used to examine differences in the means for the rTMS post 1 (acute) and post 2 (lasting) time periods. The HLM methodology will estimate the means and standard errors for all these contrasts of interest with a Bonferroni comparison procedure to adjust for the multiple contrasts.

Power Estimates

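### Contrasts 1 and 2 estimate the total effect of adding tDCS before rTMS, not the modification of rTMS-induced LTD that Aims 1 and 2 ask about, and the recording that would show the tDCS effect has no prespecified contrast

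*Combined protocol and SAP*

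**What the plan says.** Specific Aim 1 is to "Determine in normal healthy subjects how increased activation of the TC modifies the induction of LTD by 1 Hz and 10 Hz rTMS". Aim 2 asks the same with the DLFC preconditioned, and adds: "We predict that rTMS delivered to the TC will induce LTD in the DLFC after it has been preconditioned with tDCS".

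Under Data Analysis (Analyses and Power calculations), the primary outcome is "a difference score between sham and active rTMS in the LMFP of TEPs (Δ LMFP) recorded from TC and DLFC". Contrasts 1 and 2 compare sham with active tDCS within 1 Hz and within 10 Hz. Contrasts 3 and 4 compare the two frequencies under sham and under active tDCS. Six further contrasts concern the two post-rTMS recordings, and a Bonferroni adjustment is applied.

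No within-session reference recording is named. Study endpoints in the Protocol Summary says LMFP is "measured at baseline and after sham and active treatment conditions", without saying whether or how baseline is subtracted.

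Study visits and Table 1 schedule four TMS/EEG recordings per session: before tDCS, after tDCS, after rTMS, and after a further delay. Subject flow lists three conditions: sham/sham, sham/active and active/active.

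The section on the test articles says of tDCS: "At 2 mA and no longer than 20 minutes duration, there is a net increase in excitability under" both electrodes. From modelled fields it adds that "preconditioning of the TC should not increase activation of the DLFC and vice versa". Scientific Premise says: "It is critical, therefore, to develop a method for measuring homeostatic plasticity, which we propose to do using TEPs". The section on what is unique says TEPs "will be used to physiologically confirm the effects of our interventions by measuring electrical activity directly from the cortex".

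**The concern.** The question in Aims 1 and 2 is an interaction: does preactivation change what rTMS does? Answering it directly needs the rTMS effect (active minus sham) at each tDCS level. The design provides it only under sham tDCS, because no session pairs active tDCS with sham rTMS. Any after-effect of tDCS on LMFP therefore sits inside contrasts 1 and 2 together with the modification of interest.

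The protocol expects the two to have opposite signs: LTD lowers excitability, while 2 mA tDCS raises it. The overlap matters most in the preconditioned region, which is TC in Aim 1 and DLFC in Aim 2. The DLFC is where Aim 2's main prediction lies. If the contrast is read as the modification of LTD, a null or positive result could be misread. The recording that would show whether preactivation occurred, and how large it was, is collected but enters no stated contrast.

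**Working it through.** **The plan's own figure.** Power Estimates gives 99% for contrast 1, acute, from means .89 and .64, SD .08, two-sample t, n=5. The significance level is not stated; I assume two-sided 0.05. The difference is .89 − .64 = .25, or .25/.08 = 3.125 SD. The noncentrality is 3.125 × √(5/2) = 4.94 on 8 df, which gives 99.0%. The stated effect size of 2.95 gives 98.2%. The figure reproduces and is not in dispute.

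**Notation, at the post-rTMS recording, relative to the sham/sham session.**
- R: rTMS effect without tDCS.
- I: change in the rTMS effect caused by preactivation, the target of Aims 1 and 2.
- T: tDCS after-effect at the post-tDCS/pre-rTMS recording.
- k: fraction of T that would persist to the post-rTMS recording *without active rTMS*. If active rTMS reverses raised excitability, that reversal is the hypothesised effect and belongs in I, not in k.

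**Cell means** (randomised order, no carry-over, sham tDCS inert): SS = 0, SA = R, AA = R + I + kT.

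**Contrasts 1 and 2**
- Raw or pre-tDCS reference: (AA − SS) − (SA − SS) = AA − SA = I + kT.
- Post-tDCS reference: I + kT − T = I − (1 − k)T.

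The first equals I only if kT = 0, the second only if k = 1 or T = 0.

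**Contrast 3:** (SA − SS) at 1 Hz minus the same at 10 Hz = R₁ − R₁₀, which contains no T.

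**Contrast 4:** (R₁ + I₁ + kT₁) − (R₁₀ + I₁₀ + kT₁₀), which is free of kT only if kT is equal in the two frequency groups.

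**Size, in units of T, raw or pre-tDCS reference**

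| True I | k = 1 | k = 0.5 | k = 0 |
|---|---|---|---|
| −T | 0 | −0.5T | −T |
| 0 | +T | +0.5T | 0 |

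A real modification of size T is fully hidden only if the after-effect persists in full.

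**Illustration.** The documents give no tDCS effect on TEPs, so kT is assumed. With I = 0, a raw-scale SD, two-sample t, n=5 and two-sided 0.05 (critical value 2.306), the noncentrality is (kT/SD) × √2.5.

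| kT (SD) | Significant increase | Significant decrease |
|---|---|---|
| 0 | 2.5% | 2.5% |
| 0.25 | 5.4% | 1.0% |
| 0.5 | 10.4% | 0.4% |
| 1 | 28.6% | 0.04% |

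This follows the plan's two-sample simplification. Contrasts 1 and 2 are within-subject, so the rates show direction and order of size, not the behaviour of the planned hierarchical model.

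**The case against.** Active/active minus sham/active is a legitimate quantity. Power Estimates treats LTD as a fall in amplitude, which suits a total effect, and Aim 2's prediction can be read as concerning the active/active response. Study endpoints leans towards a baseline reference. Nulls are weak evidence here anyway: the plan itself states 6% power for the 5 Hz basis of contrast 2 acutely and 48% for contrast 1 at 30 minutes. Nowhere does it promise to report a null as absence of modification. All of this stands, and it is why the remedy is labelling and interpretation rather than a new design. It does not remove the mismatch, because both aims ask how activation modifies LTD and a baseline reference still gives I + kT.

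A reader might infer more than the documents support:
- *The tested contrast tends to produce false LTD findings.* It does not under the protocol's own expectation. T above zero makes it conservative in the LTD direction, as the last column of the illustration shows.
- *The 99% power is overstated because tDCS masks the effect.* This cannot be shown. The .25 difference may already be a total effect, and Power Estimates says TEP data do not exist.
- *Referencing to the post-tDCS recording would isolate I.* It would not. If the after-effect decays, that contrast is biased towards apparent LTD. Any resulting false-LTD rate would describe that alternative, not the plan's test.
- *TEPs after tDCS have no role, or the after-effect is confined to one region.* Both are too strong. TEPs have a stated confirming role but no prespecified contrast for it, and minimal overlap is a modelling result.

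**Conclusion.** The point holds as an interpretive gap in the primary analysis. Contrasts 1 and 2 reduce to active/active minus sham/active. On the raw or pre-tDCS scale that is I + kT, the total effect of adding tDCS before rTMS. This follows from the three-session design and needs no assumed value.

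Its practical size is kT, which the documents do not give. Because kT is unknown, a null does not show absence of modification and an increase does not show that tDCS blocked LTD. A significant decrease would still support the hypothesis, provided the after-effect is not itself negative, which the proposed check would show. Contrast 3 is unaffected, and contrast 4 is affected only if kT differs between frequency groups.

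The conclusion rests on randomised order, adequate washout and an inert sham tDCS. It should be fixed before analysis, but it does not invalidate the tested contrast.

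**What to change.** In Data Analysis, using recordings already scheduled:

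1. Name the pre-tDCS recording as the within-session reference for Δ LMFP. Keep active/active minus sham/active as tested contrasts 1 and 2, and label them *total effect of adding tDCS before rTMS*.
2. Prespecify post-tDCS minus pre-tDCS LMFP, active versus sham tDCS, by region, as the manipulation check and estimate of T. It precedes rTMS, so it can use all 10 subjects per aim (one active-tDCS and two sham-tDCS sessions each).
3. State that neither a null nor a positive contrast 1 or 2 in the preconditioned region will be interpreted as absence or blocking of LTD modification without reference to that check.

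Optional: report the same contrasts on post-rTMS minus post-tDCS LMFP, descriptively only. State that they estimate I − (1 − k)T, with k meaning persistence without active rTMS, and that they lean towards apparent LTD if the after-effect decays. Table 1 places the post-rTMS recordings at 80 and 130 minutes, 40 and 90 minutes after the post-tDCS recording at 40, so decay is a practical issue.

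Cost: slightly more analysis and a more limited conclusion. No new visits, recordings or subjects are needed. I itself remains unidentified, since separating it would need an active-tDCS/sham-rTMS session, which is not requested here.

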Study Design, Population, Apparatus and Investigational Plan

Aims 1 & 2.

Design: This is prospective, experimental design includes a block randomized, blinded, sham controlled, mixed effects model with sequential assignment to two treatment arms (1 or 10 Hz rTMS) and random assignment to three experimental conditions within each arm (Table 1).

Randomization: Subjects will be assigned sequentially to one of two parallel groups (1 Hz or 10 Hz rTMS: Table 1.5). Next, they will complete three experimental test sessions (Table 1). The order of test sessions is randomized. A minimum two week washout period will follow each session to minimize session to session carry forward effects.¹⁵ Washout can exceed two weeks.

[figure not shown]

Figure 1.5. Subject flow.

Study visits: Study visits will be to the transcranial magnetic stimulation laboratory, room 654-2, located on the 6th floor of the Biomedical II research building on the UAMS

Study Title: Regulating homeostatic plasticity and the physiological response to rTMS
 PI: [name]
 Institution: University of Arkansas for Medical Sciences
 Support: Department of Neurobiology and Dev. Scs.

campus. In total, there will be 4 study visits - 1 consent/screening visit and 3 laboratory visits per subject. The 3 laboratory study visits will be separated in time by a minimum of two weeks. The time required to complete a study visit ranges from 1 hour, when TMS/EEG is not collected, to 3.5 hours, when TMS/EEG is collected. TMS/EEG is recorded immediately before and after tDCS preconditioning, immediately following rTMS and after a 20-30-minute delay to examine the acute and lasting effects.

Subject flow: Twenty healthy subjects who meet the entry criteria and pass safety screening for tDCS and TMS will be enrolled (Figure 1.5). Ten subjects will be tested in each aim, with two parallel groups of 5 subjects receiving either 1 or 10 Hz rTMS. Two randomization lists of 10, each balanced between tDCS over TC and tDCS over DLFC, were generated based

on uniformly distributed random number generation in SAS v9.4. The first 10 recruited subjects will receive 1Hz rTMS treatment while the second 10 will receive

Experimental conditions & TMS/EEG assessments.								
Condition†	TMS/EEG	tDCS	TMS/EEG	rTMS	TMS/EEG	30 min delay	TMS/EEG	
1		sham		sham				
2		sham		active				
3		active		active				
Time (mins)	0	20	40	60	80	100	130	

Table 1. † The order of conditions is randomized. A 2 week washout separates each condition.

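### Aims 1 & 2 record LMFP before stimulation in every session, but the written analysis names no baseline term; adding one is a cheap gain in precision of uncertain size

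*Combined protocol and SAP*

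**What the plan says.** - **Recordings.** Study visits (Aims 1 & 2): "TMS/EEG is recorded immediately before and after tDCS preconditioning, immediately following rTMS and after a 20-30-minute delay". Table 1 shows the first of these at time 0 in all three conditions (sham/sham, sham/active, active/active, naming tDCS then rTMS).
- **Spacing.** Same section: "The 3 laboratory study visits will be separated in time by a minimum of two weeks".
- **Response.** Data Analysis, Analyses and Power calculations, repeated in the Protocol Summary: "a difference score between sham and active rTMS in the LMFP of TEPs".
- **Model.** "Hierarchical Linear Models (HLMs) will be used due to the nested structure of the design", and "HLMs will fit the complex covariance structure of the dosing schedule", described as tDCS condition within rTMS frequency. There are four main contrasts, six more on "differences in the means for the rTMS post 1 (acute) and post 2 (lasting) time periods", and a Bonferroni adjustment. No baseline covariate, change from session baseline or pre-stimulation time level is named.
- **Hints of a baseline.** The Protocol Summary endpoints say that the outcome is "measured at baseline and after sham and active treatment conditions", and the Objectives describe the outcome as a change in cortical excitability. Neither says how the baseline enters the analysis.
- **Aim 3.** The same symbol, Δ LMFP, there means change from baseline.

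**The concern.** Subtracting one session from another within a subject removes stable differences between subjects. It does not remove what differs between two laboratory days, such as electrode contact, residual coil placement error, a motor threshold that is reset each session, and resting excitability. The time-0 recording captures part of that variation before the session's stimulation begins. The Scientific Premise itself attributes variable responses to unknown baseline excitability and argues for measuring it.

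The stake is precision. The main contrasts rest on five subjects per cell and face a multiplicity adjustment. If the time-0 value predicts the post-rTMS value within a subject, leaving it out gives up power that needs no new recording.

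**Working it through.** **1. What the contrasts contain.** Write SS, SA and AA for the three sessions. Under sham tDCS, Δ = SA − SS; under active tDCS, Δ = AA − SS. Contrasts 1 and 2 are therefore (AA − SS) − (SA − SS) = AA − SA. The subject effect and the sham/sham session cancel; the session-level errors of two separate days remain. With session-level variance set to 1 and n = 5, the variance is 2 × 1/5 = 0.40. Contrasts 3 and 4 compare SA − SS or AA − SS between frequency groups, so there the sham/sham session does not cancel.

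**2. The plan's own power.** Power Estimates uses two-sample t-tests with n = 5. Two-sided 0.05 is assumed because alpha is not stated. The noncentrality is d × √(n/2), on 8 df.
- 1 Hz acute: d = 2.95 gives 98.2%; the stated means and SDs give d = (0.89 − 0.64)/0.08 = 3.125 and 99.0%. The stated 99% reproduces.
- 1 Hz at 30 minutes: d = 0.95 gives 26%, not the stated 48%, which needs d of about 1.37. Both values are carried below as illustrations; 1.37 is back-solved, not planned.

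**3. Effect of using baseline.** Let ρ be the within-subject, session-level correlation between time-0 and post-rTMS LMFP. The documents give no value, so a range is assumed. Relative to post-only, the standard error is √(2(1 − ρ)) for change from baseline and √(1 − ρ²) for a covariate, before its df cost.

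| ρ | change from baseline | covariate |
|---|---|---|
| 0.3 | 1.18 | 0.95 |
| 0.5 | 1.00 | 0.87 |
| 0.7 | 0.77 | 0.71 |

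A change score gains nothing until ρ exceeds 0.5.

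**4. The plan's two-sample method with the covariate** (d/√(1 − ρ²), 7 df).

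| alpha | d | none | ρ = 0.3 | ρ = 0.5 | ρ = 0.7 |
|---|---|---|---|---|---|
| 0.05 | 0.95 | 26% | 28% | 32% | 44% |
| 0.05 | 1.37 | 48% | 50% | 58% | 74% |
| 0.005 | 2.68 | 65% | 65% | 76% | 92% |
| 0.005 | 2.95 | 76% | 76% | 85% | 96% |

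The 0.005 rows are 0.05/10, for four plus six contrasts. At that alpha, d = 0.95 only moves from 5.1% to 6.6% at ρ = 0.5. With ρ = 0, d = 2.68 falls from 65% to 60% and d = 2.95 from 76% to 71%.

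**5. The crossover itself.** Simulation used three sessions per subject, one post value per session, subject effects, cells of five, one common slope and two-sided 0.05, with d in units of the session-level SD. Results at ρ = 0.5 for AA − SA in one cell:

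| model | variance | power, d = 0.95 | power, d = 1.37 |
|---|---|---|---|
| both aims, 20 subjects | 0.40 to 0.31 | 32% to 38% | 55% to 65% |
| one aim, 10 subjects | 0.40 to 0.33 | 30% to 37% | 53% to 62% |

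The variance reductions are 0.09/0.40 = 22% and 0.07/0.40 = 18%. Type I error stayed near 5%. At ρ = 0.3 the gain is about 0 to 2 points; at 0.7, about 20 to 27; at zero, a loss of about 1 to 3.

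**6. Two conditions on the gain.** With the slope fitted inside a single cell of five, ρ must reach about 0.6 to repay the degree of freedom (37% with and without the covariate at d = 0.95). With ρ = 0.5 in sham-tDCS sessions and 0 in active-tDCS sessions, a common slope moves the variance only from 0.40 to 0.395; with +0.3 and −0.3 it rises from 0.41 to 0.43.

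**The case against.** The strongest reply is that silence is not a decision. A reader might infer that the plan has chosen to discard its baseline recordings and analyse raw post-rTMS values. The documents do not support that: the endpoint text mentions a baseline measurement, the Objectives speak of change, and nothing says that the subtracted quantity is uncorrected. What stands is narrower: the analysis section, where the baseline would have to appear, does not say how it is used.

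Second, the size is unknown. The assessment-tool section describes TEPs as highly repeatable, and coil position is tracked stereotaxically, so session noise may be small. This stands as a limit on the gain; the cost in that case is also small.

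Third, the protocol's theory holds that the starting state governs the direction of the rTMS response and that tDCS stabilises it. That makes unequal slopes by tDCS condition plausible, and step 6 shows that the gain can then vanish. This also stands, and is why a slope check is needed.

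Fourth, a reader might infer that adjustment cannot introduce bias because time 0 precedes treatment. It precedes that session's treatment only. In sessions 2 and 3 it follows earlier stimulation, so the adjustment relies on the two-week washout.

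Finally, this is a pilot meant partly to collect TEP data for later power calculations. That lowers the urgency, but the same model would also estimate the baseline slope that such planning needs.

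**Conclusion.** The point holds as a precision improvement, not as an error in the plan. A pre-stimulation LMFP exists for every Aims 1 & 2 session, the written analysis names no baseline term, and the contrasts carry session-level variation with five subjects per cell.

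Under an assumed correlation of 0.5 and one common slope, contrast variance falls by roughly 20%, worth about 6 to 10 points of power at d = 0.95 to 1.37. The gain is close to nil at 0.3, substantial at 0.7, and little or none if slopes differ strongly between sham and active tDCS. The downside at zero correlation is about 1 to 3 points in the crossover model, or about 5 points at 0.005 under the two-sample approximation. All of this assumes that effect sizes taken from published motor evoked potential data carry over to LMFP, which the documents cannot confirm.

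**What to change.** In Analyses and Power calculations:

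1. Define Δ LMFP for Aims 1 & 2 and distinguish it from its Aim 3 meaning.
2. Fit the hierarchical model to post-rTMS LMFP for each recording site, with a subject effect, condition (SS, SA, AA) within frequency, and post 1/post 2 as a time factor, allowing for the two post values that share a session.
3. Add the same session's time-0 LMFP from the same site, split into the subject's mean and the session's deviation from it, with one common slope. Do not use the post-tDCS recording as this covariate, because active tDCS may already have changed it.
4. Obtain contrasts 1 to 4 as linear combinations that keep the subtraction of the sham/sham session, so the questions asked do not change.
5. As a sensitivity analysis, let the slope differ by tDCS condition. State that time-0 values in sessions 2 and 3 rely on the washout.

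The cost is a rewritten model paragraph and about one error degree of freedom, with no new recordings or visits. It should be fixed before unblinded data are seen, so that the choice of baseline handling cannot depend on the results.
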